**List of Abbreviations****LIST OF ABBREVIATIONS**

AE	Adverse Event/Adverse Experience
CFR	Code of Federal Regulations
CRF	Case Report Form
DSMP	Data and Safety Monitoring Plan
FDA	Food and Drug Administration
GCP	Good Clinical Practice
HIPAA	Health Insurance Portability and Accountability Act
IB	Investigator's Brochure
IND	Investigational New Drug Application
IRB	Institutional Review Board
PHI	Protected Health Information
PI	Principal Investigator
SAE	Serious Adverse Event/Serious Adverse Experience
SOP	Standard Operating Procedure

## Study Summary

Title	A Prospective, Open-Label, Parallel Study Evaluating the Effect of an Adjunctive Anti-Seizure Medication using a Glutamatergic Modulator in Patients with Focal Epilepsy and High-Grade Glioma
Running Title	Adjunctive Anti-Seizure Drug (ASD) in Drug-Resistant Focal Epilepsy and high-grade glioma
Protocol Number	19-006286
Phase	IV (investigator-initiated)
Methodology	This is an open-label, parallel study evaluating the effect of PER in patients with biopsy-proven high-grade glioma (grade II and above) and focal epilepsy. Dose ranging will be based on best clinical practice in patients with drug-resistant focal epilepsy.
Overall Study Duration	18 months
Subject Participation Duration	Subject will participate in study procedures for a total duration of 12 months including a 2-to-4-week titration phase, 12-week minimum and 24-week maximum stable treatment phase for interim analysis, and 40 weeks of total treatment time at study termination.
Single or Multi-Site	Single Site
Primary Objectives	To evaluate the efficacy and safety of PER on seizure frequency in adult patients with biopsy-proven high-grade glioma and focal epilepsy compared with alternate ASDs.
Secondary objectives	To assess the progression of biopsy-proven high-grade glioma in patients prescribed a daily dose of 4-8mg of PER for 40 weeks in patients with focal epilepsy when compared with alternate ASD  To assess the change in neurocognitive function and brain MRI progression over the course of PER treatment with a daily dose of 4 mg (up to - 8mg) in patients with biopsy-proven high-grade glioma and focal epilepsy compared with alternate ASDs.  To identify a biomarker-specific response to seizure-reduction in patients treated with PER in patients with a biopsy-proven high-grade glioma (i.e., IDH-mutant vs wildtype).

Number of Subjects	20
--------------------	----

Diagnosis and Main Inclusion and Exclusion Criteria	
Inclusion Criteria
 
The subject, or the subject's legally acceptable representative is willing to participate in a clinical trial, provides written informed consent, and subject provides written assent, as required by the Mayo Clinic Institutional Review Board (IRB) policy involving human subjects.
 
 
1. Subjects that satisfy the following diagnostic criteria: Patients with established clinical diagnoses, of high-grade glioma (WHO class II and above) and epilepsy refractory to at least one ASD, with a seizure frequency of at least 1 seizure per 3-months during baseline.
 
2. Subjects with body weight of <math>\geq 40</math> kg and <math>\leq 125</math> kg at screening
 
3. Adults age 18 and older
 
 
Exclusion Criteria
 
 
A. Subject has serious cardiac, respiratory, renal, gastrointestinal, hematologic, or other medical condition as determined by the investigator to potentially interfere with the study
 
B. Subjects with high-grade glioma not following Stupp protocol for treatment of glioblastoma.
 
C. History of status epilepticus in the 6 months prior to screening or a history of seizure clusters progressing to status epilepticus.
 
D. Past medical history of drug and/or alcohol abuse
 
E. Pregnant or breast-feeding
 
F. Subjects treated with PER prior to baseline
 
G. Prior felony conviction disclosed by the patient or previously stated in medical record.
 
H. History of violent behavior
 
I. Clinically significant laboratory abnormality at screening or baseline visits, as determined by the investigators
 
J. Use of an investigational drug or device within 20 days prior to treatment Day 1
 
K. Repeated radiation therapy for tumor regrowth
 
L. Subjects that plan to undergo tumor resection on or after baseline visit
 
M. Uncontrolled psychiatric disorder at baseline
 
N. Subjects who report active suicidal attempts or suicidality including subjects with a history of suicide attempts or suicidality determined to be
 

	
clinically significant by investigators at screening.
 
O.

--	--

Study Product, Dose, Route, Regimen	PER is a noncompetitive AMPA glutamate receptor antagonist. The two phases of the treatment portion of this study include a titration phase and a stable dosing phase. This study will have two treatment arms consisting of PER and alternative ASD arm. The PER arm will begin a titration phase with 2mg PER PO q.d. (may be split to b.i.d.) for one week and increase by 2mg/week until reaching an initial dose of 4mg PO q.d. (q.d. or b.i.d. dosing) is reached. Flexible dosing of PER above 4mg to a maximum of 8 mg daily will be compared to use of alternative ASDs and be guided by best clinical practices with dosing and indication within U.S. FDA guidelines.
Duration of Administration	Participants will be assigned to receive open label PER or an alternate ASD for at least 12 week and up to 40weeks for the remainder of the study. This includes 2-4 weeks of titration and up to 40 weeks of stable dosing. Reduction by 2 mg will be allowed in cases of efficacy if doses greater than 4 mg daily result in non-idiopathic side-effects.
Reference therapy	All comparisons will use standard ASDs as the reference therapy using an intent to treat study design for patients initiating or tapering off PER therapy.
Statistical Methodology	Statistical analysis will include Student T-test, Chi-square for categorical differences. An interim analysis will be performed when half of the targeted subjects are enrolled.

## 1 Introduction

This document is a clinical research protocol for a human research study. This study will be carried out in accordance with the applicable United States government regulations and Mayo Clinic research policies and procedures.

### 1.1 Background

Does the novelty of Perampanel's unique mechanism of action demonstrate anti-seizure efficacy, tumor-cytotoxic activity, and impact progressive impairment in neurocognitive function in patients with high-grade glioma? The major reasons why this study should be conducted include:

1. Seizures commonly occur in 40% to 70% of patients with a primary brain tumor/glioma.
2. PER is FDA approved for adults with focal seizures.

3. PER has novel and unique mechanisms of action that include a primary effect on excitatory amino acids/AMPA.
4. Glutamate-induced excitotoxicity and disruption of intracellular communication hold a key role in the progression of disease in patients with glioblastoma (altered cysteine-glutamate transport).
5. Glutamate induced over-activity is also suspected to influence high-grade glioma growth.
6. Studies show that isocitrate dehydrogenase 1 (IDH1) mutant gliomas are more likely to cause seizures than IDH1 wild-type gliomas. The IDH1 mutation has been associated with tumorigenesis and has implications relative to differential treatment for primary brain cancer and prognosis.

Because of shared pathways, current anti-seizure drugs (ASDs) may affect treatment of patients with brain tumor, and various antitumor therapies are valuable for seizure management. Mechanisms involving cysteine-glutamine transporters, for example, regulate glutamate release and return through cellular exchange. One explanation for the close link between seizures and glioma evolution are elevated extracellular glutamate levels in the peri-glial and -neuronal space with ensuing over-activity of  $\alpha$ -amino-3-hydroxy-5-methyl-4-isoxazolepropionic acid (AMPA) and N-methyl-d-aspartate (NMDA) receptors in both conditions. Recent studies point to the role of glutamate in excitotoxic damage resulting in seizures as well as maintenance and invasion of malignant glioma. Blockade of this system could lead to pharmaceutical development that could affect the excitotoxicity of both high-grade glioma and brain-tumor related epilepsy. Human trials of PER demonstrate safety and efficacy as an adjunctive therapy for adult patients with epilepsy. Limited information is available to demonstrate effectiveness in subpopulations associated with excessive glutamatergic stimulation such as brain tumor. PER, a FDA approved AMPA antagonist cleared for clinical use, may have immediate impact in 80,000 patients with brain tumors, and 3.4 million Americans with epilepsy (commonly co-morbid conditions). Anecdotal benefit has been reported in epilepsy patients with primary brain tumor and low dose PER (Vecht et al., 2017). Cognitive decline frequently complicates treatment of patients with high-grade glioma and also in patients with epilepsy impairing overall QoL.

## 1.2 Investigational Agent

Participants will be assigned to receive open label PER or an alternate ASD for 40 weeks. The route of drug delivery will be orally administered (PO).

## 1.3 Preclinical Data

Because of shared pathways, current anti-seizure drugs (ASDs) may affect treatment of patients with brain tumor, and various antitumor therapies are valuable for seizure management. Mechanisms involving cysteine-glutamine transporters regulate glutamate release and return through cellular exchange. Blockade of this system could lead to pharmaceutical development that could affect the excitotoxicity of both high-grade glioma and other brain-tumor related epilepsy syndromes. Limited information is available to demonstrate effectiveness in subpopulations associated with excessive glutamatergic stimulation such as brain tumor.

## 1.4 Clinical Data to Date

Human trials of PER have demonstrated its efficacy as an adjunctive therapy for adult patients with epilepsy. Furthermore, Anecdotal improvements in both seizure frequency and tumor progression have been reported in epilepsy patients with primary brain tumors on low-dose PER (Vecht et al., 2017).

## 1.5 Dose Rationale

We will follow FDA recommendations for dosing of PER^14. As such, patients will begin on PER 2 mg PO and increase in weekly intervals of 2 mg/week until reaching minimum dose of at least 4 mg/day and a maximum of 8 mg/day per patient. Alternative ASDs will be instituted according to best clinical practice and without excessive dosing beyond standard doses approved by the U.S. Food and Drug Administration. Participants will be assigned to receive open label PER or an alternate ASD for 40 weeks. The frequency of oral delivery of PER will be every 24 hours but no more frequently than every 12 hours. The route of drug delivery will be orally administered (PO). The other ASD will be chosen and be administered according to prior exposure to ASDs and according to best clinical practice.

## 1.6 Risks and Benefits

Side effects associated with PER include anxiety, dizziness, headache, irritability, problems with coordination and balance, sleepiness, nausea, and weight gain. Serious side effects observed in clinical trials for patients taking PER include psychiatric and behavioral problems consisting of aggression, hostility, anger, and suicidal thoughts or behavior. In response to these psychiatric and behavioral risks that have been associated with patients beginning PER or taking increased doses of the drug, individuals who disclose history of prior felony conviction or who have violent behavior present in historical review will be excluded from the study. Additionally, any patients with clinically significant suicide risk (e.g., suicide attempt in the past 5 years or active suicidality as judged by the clinician) will be excluded from the study. Patients will be screened and monitored for changes in psychological status and behavior using the Neurological Disorders Depression Inventory for Epilepsy (NDDI-E), PHQ-9, Columbia-Suicide Severity Rating Scale (C-SSRS), and Quality of Life in Epilepsy Inventory (QOLIE-31) throughout the study. Patients' status will be closely monitored by the physicians throughout the study with the low probability of developing these side effects outweighed by the benefits PER can provide to patients.

## 2 Study Objectives

### Primary Objective

Demonstrate the efficacy and safety of PER on seizure frequency in adult patients with biopsy-proven high-grade glioma and focal Epilepsy compared with alternate ASDs.

### Secondary Objective

To assess the change in neurocognitive function and brain MRI progression over the course of PER treatment with a daily dose of 4 mg (up to -8mg) in patients with biopsy-proven high-grade glioma and focal epilepsy compared with alternate ASDs.

To identify a biomarker-specific response to seizure-reduction in patients treated with PER in patients with a biopsy-proven high-grade glioma (i.e., IDH-mutant vs wildtype).

## 3 Study Design

### 3.1 General Description

This study is a prospective, open-label trial evaluating the effectiveness of PER on seizure frequency in adult patients with brain-tumor with seizures associated with high-grade glioma. Subjects (n = 20) will be male and female adults with a high-grade glioma recruited from Mayo Clinic in Jacksonville, Florida-[name], DO, (PI). Participants included will have had uncontrolled seizures, on a current regimen of at least 1 ASD manifesting ongoing focal seizures (including focal aware motor, focal impaired

awareness, and focal to bilateral tonic-clonic seizures), with at least 1 seizure/month during a retrospective 2-month baseline, relative to the screening visit.

All patients included in the study will follow STUPP protocol (radiotherapy plus concomitant and adjuvant Temozolomide) for treatment of high-grade glioma in addition to best medical practice of comorbidities, as is standard-of-care.

### **3.2 Number of Subjects**

20

### **3.3 Duration of Participation**

12 months

### **3.4 Primary Endpoints**

- A. The number of patients with a high-grade glioma who achieve a > 50% reduction in focal seizures with PER 4 mg daily after failing 1 or more ASDs at 3 and 6 months.
  1. The overall survival of patients with high-grade glioma treated with PER at 3 months.
  2. Decline in neuropsychological function at 6 months.

All comparisons will use intent to treat model for patients initiated or exiting PER therapy. In event of patients not surviving till 12 months, most recent data prior to death will be used for correlation.

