#### **4.3 Subject Recruitment, Enrollment and Screening**

Subjects (n = 20), will be male and female adults with a high-grade glioma recruited from Mayo Clinic in Jacksonville, Florida- [name], DO, (PI). 10 subjects will be enrolled into an adjunctive Perampanel and other ASDs group, and 10 subjects will receive only alternative ASDs. There will be a 6-month recruitment period for screening and enrollment. The treating physician will decide, based on best medical practice, which patients are candidates for adjunctive Perampanel and other ASDs, or only alternative ASDs. Patients taking Perampanel will begin their titration phase upon enrollment.

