### 7.2 Statistical Methods

#### Descriptive Statistics

Statistical analysis will include Student T-test, Chi-square for categorical differences. An interim analysis will be performed when half of subjects are enrolled.

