#### Handling of Missing Data

Study data will be collected and managed using REDCap electronic data capture tools hosted at Mayo Clinic. All data requested on the Case Report Form (CRF) will be recorded for each participant. A standardized CRF will be generated by REDCap. For any data query, the Principal Investigator and Investigators will meet to clarify the data queried and make corrections based on consensus. Once the study is completed, the Principal Investigator will randomly select 3 participants and compare the data documented for each on the CRF with what is entered into the REDCap database. If there is any discrepancy, the Principal Investigator and/or Investigators will cross-reference all 20 patients to ensure accuracy.

**Primary Hypothesis:** We hypothesize that perampanel will lead to a significant reduction in seizure frequency for adult patients with brain tumor-related seizures associated with high-grade glioma.

We will compare seizure frequency before and 3 months after treatment with monotherapy and adjunctive PER and use descriptive statistics to demonstrate differences in responders. A P-value < 0.05 will be used to reflect statistical significance.

**Secondary Hypothesis 1:** We hypothesize the progression of brain tumor (comparing 4 and 8 mg/d of perampanel) based upon fusion by comparing baseline brain MRI and MRI at 12 months will be less for IDH-mutants.

We hypothesize there will be minimal or no change in neurocognitive function from 0 to 3 months on Montreal Outcome Cognitive Assessment (MOCA; higher scores indicating greater function); and the Clinical Global Impression of Change (CGIC; scores from 1 to 7, with lower scores indicating greater improvement and a score of 4 indicating no change).

Chi-square and Student T-test will be used to measure differences in assessment and change during the study period. A P-value < 0.05 will be considered significant.

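### Section 3.4 lists four results as primary, in conflict with sections 2 and 7.2, and the plan gives only an unadjusted 0.05 threshold; testing all four would carry up to about a 19% chance of a false positive

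*Combined protocol and SAP*

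**What the plan says.** Section 3.4 (Primary Endpoints) has item A, patients with more than a 50% "reduction in focal seizures with PER 4 mg daily after failing 1 or more ASDs at 3 and 6 months". Two numbered items sit beneath it: "The overall survival of patients with high-grade glioma treated with PER at 3 months" and "Decline in neuropsychological function at 6 months". The section marks none of these as the single primary result.

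Section 2 and the Study Summary give one primary objective: efficacy and safety of PER on seizure frequency, compared with alternate ASDs. Both place neurocognitive change among the secondary objectives. Neither lists survival as an objective.

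Section 7.2 states one primary hypothesis, a significant reduction in seizure frequency. The analysis (printed under the missing-data subheading) reads: "We will compare seizure frequency before and 3 months after treatment with monotherapy and adjunctive PER". The same sentence says that differences in responders will be shown descriptively. Then comes "A P-value < 0.05 will be used to reflect statistical significance".

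After the secondary hypothesis and the 0-to-3-month MOCA and CGIC text, chi-square and t-tests of assessments and change are planned, with "A P-value < 0.05 will be considered significant". The general methods statement is "Statistical analysis will include Student T-test, Chi-square for categorical differences".

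On group sizes, section 4.3 says "10 subjects will be enrolled into an adjunctive Perampanel and other ASDs group, and 10 subjects will receive only alternative ASDs". Section 7.1 calls the study a pilot that is not powered for effectiveness. The documents contain no multiplicity rule, and they plan one interim look at safety and efficacy without an alpha rule.

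**The concern.** A reader of section 3.4 alone finds four results with equal claim to be primary. A reader of section 7.2 finds a fifth measure, 3-month seizure frequency, attached to the primary hypothesis. The two sections do not name the same primary outcome, so it is not settled in advance which result answers the study's question.

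The only rule offered for calling a result significant is an unadjusted 0.05. If several of the listed results are tested against it, the chance that at least one crosses by luck rises above 5%, and a seizure result could be chosen as the primary one after the data are seen. This matters because section 7.1 says the pilot is meant to inform whether a larger multi-center trial is supported, and section 13 plans publication.

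**Working it through.** The documents state no family-wise error rate, so there is no figure of the plan's own to reproduce.

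**1. Where the sections disagree**

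| Result | Section 3.4 | Section 2 | Section 7.2 |
|---|---|---|---|
| Responders, 3 months | Primary | Not named (objective is seizure frequency) | Responders described; no test tied to them |
| Responders, 6 months | Primary | Not named | No test or threshold tied to it |
| Survival, 3 months | Primary | Not named | No test or threshold tied to it |
| Neuropsychological decline, 6 months | Primary | Neurocognition is secondary | MOCA and CGIC at 0 to 3 months, after the secondary hypothesis |
| Seizure frequency, before versus 3 months | Not listed | Primary (no time point) | Primary hypothesis, P<0.05 |

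**2. Size if all four listed results were tested**

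Inputs: k = 4 results (section 3.4) and threshold 0.05 (section 7.2). Independence and an exact 5% size for each test are assumptions.

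- Independent tests: 1 − (1 − 0.05)^4 = 1 − 0.8145 = 18.5%.
- Upper bound under any dependence, single final analysis: 4 × 0.05 = 20%.

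**3. Effect of correlation** (the documents give none; values assumed; simulated two-sided z-tests, k = 4)

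- All four equally correlated at 0.3, 0.5, 0.7 and 0.9: 17.4%, 15.6%, 13.0% and 9.3%.
- Only the two responder time points correlated, at 0.5, 0.7 and 0.9: 17.9%, 17.3% and 16.2%.

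**4. Effect of discrete tests at 10 versus 10** (section 4.3; event rates assumed)

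The true size of an uncorrected chi-square test at nominal 0.05 is 2.99% for a 20% response rate and 4.22% for 50%. For 3-month death rates it is 0.12% at 5% and 2.99% at 20%. Taking two responder tests, one survival test and a neuropsychological t-test at 5%, all independent:

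- Lowest case (response 20%, death 5%): 1 − (0.9701)²(0.9988)(0.95) = 10.7%.
- Highest case (response 50%, death 20%): 1 − (0.9578)²(0.9701)(0.95) = 15.5%.
- The same range of cases with Yates correction or Fisher's exact test: 6.5% to 8.1%.

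**5. Effect of the interim look**

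If efficacy were also tested at an unadjusted 0.05 at half the information (an assumption; the protocol says only when half are enrolled), each test would rise to 8.3% and four independent tests to 1 − (1 − 0.0831)^4 = 29.3%.

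**6. After a fix**

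One primary outcome at one time point, tested once: 5%. Bonferroni over four results, 0.05/4 = 0.0125 each: 1 − (0.9875)^4 = 4.9% under independence and at most 5% under any dependence.

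**The case against.** The strongest reply is that the plan does rank its outcomes. Section 2, the Study Summary and the primary hypothesis in section 7.2 all put seizures first, and neurocognition is secondary in each. In section 3.4, survival and neuropsychology are nested below item A. This stands. It means that the fault is a conflict between section 3.4 and the other sections, not an absence of any ranking.

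A reader might also infer that every listed result is tested at 0.05. The documents do not say so. The first threshold follows the 3-month seizure-frequency comparison. The second follows the secondary hypothesis. No test is named for survival, which is worded for PER patients only, or for 6-month response. The error rate is therefore conditional on a reading, although 0.05 is the only threshold available to anyone who does test them.

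A reader might go on to quote 14% to 23%. Those figures are 1 − 0.95^3 = 14.3% and 1 − 0.95^5 = 22.6%, for three and five independent tests of exact size. Section 3.4 lists four results. The fifth would be 3-month seizure frequency from section 7.2, which uses the same seizure counts as 3-month response, so independence is least plausible there.

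Nor can every listed result simply be picked as a favourable one. Section 7.2 hypothesizes minimal or no neurocognitive change, so a false finding of decline would not help the drug's case.

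Finally, this is a 20-patient pilot, declared unpowered. That lowers the consequence but does not remove the point. Lack of power concerns false negatives, and section 7.2 still hypothesizes a significant reduction and sets a P-value threshold.

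**Conclusion.** The point holds as an inconsistency with a conditional error rate. Section 3.4 gives primary status to four results, sections 2 and 7.2 give it to seizure frequency, and nothing limits multiplicity.

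If all four were tested at 0.05 in a single final analysis, the family-wise error would be up to about 19% under independence, with 20% as the ceiling. Under the assumed correlations it falls to about 9% to 18%. With chi-square tests at 10 per arm it is about 11% to 15%, and with corrected or exact tests about 6% to 8%. An unadjusted interim efficacy test would push in the other direction. Every case computed exceeds 5%, but none is a best estimate, because the plan does not say which results will be tested. Pilot status makes this a change that should be made, not one that undermines the study.

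**What to change.** In sections 3.4 and 7.2, name one primary outcome at one time point and use the same measure in both. One choice consistent with the comparison in section 2 is the 3-month proportion with more than 50% reduction, PER versus alternate ASDs. Referring only to a 3-month seizure outcome would not be enough, because responder proportion and seizure frequency would both still qualify.

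Make 3-month seizure frequency, 6-month response, survival and neuropsychological change secondary, reported as estimates with 95% confidence intervals and no claim of significance. State also whether the interim look tests efficacy; the 5% rate for a single primary outcome assumes that it does not. If the sponsor prefers to keep all four as primary, a threshold of 0.0125 each is the alternative.

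The cost is wording in two sections, with no added patients, visits or procedures. The downside is that fewer outcomes can be called significant.

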### 5.2 Treatment Regimen

Patients will begin on PER 2 mg PO and increase in weekly intervals of 2 mg/week until reaching minimum dose of at least 4 mg/day and a maximum of 8 mg/day per patient. Alternative ASDs will be instituted according to best clinical practice and without excessive dosing beyond standard doses approved by the U.S. Food and Drug Administration. Participants will be assigned to receive open label PER or an alternate ASD for 40 weeks. The frequency of oral delivery of PER will be every 24 hours but no more frequently than every 12 hours. The route of drug delivery will be orally administered (PO). The other ASDs will be chosen and be administered according to prior exposure to ASDs and according to best clinical practice.

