### 5.3 Method for Assigning Subjects to Treatment Groups

Participants will be assigned to receive:

Group A: open label arm of adjunctive PER (study drug) for patients with seizures treated with at least 1 ASD administered in escalating divided doses of 2 mg/week to 4 mg daily with flexible dosing to 8 mg/day by 4 weeks. Subjects must undergo forced titration of 2 mg/week and be able to tolerate 4 mg to continue in the study. Concomitant ASD will be utilized according to best clinical practice.

or

Group B: continued open label treatment for patients with seizures treated with at least 1 ASD, as per best medical practice, without the use of PER.

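### The primary responder endpoint is worded for PER 4 mg daily, which does not fit the flexible regimen or the intent-to-treat rule, and no rule says how responders on other permitted doses are counted

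*Combined protocol and SAP*

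**What the plan says.** Primary endpoint A in section 3.4 counts patients who achieve a more than 50% "reduction in focal seizures with PER 4 mg daily after failing 1 or more ASDs at 3 and 6 months". The same section then states: "All comparisons will use intent to treat model for patients initiated or exiting PER therapy".

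The regimen is described differently. Section 5.2 (and 1.5 in the same terms) raises PER weekly "until reaching minimum dose of at least 4 mg/day and a maximum of 8 mg/day per patient". Section 5.3 gives Group A "2 mg/week to 4 mg daily with flexible dosing to 8 mg/day by 4 weeks" and requires subjects to "be able to tolerate 4 mg to continue in the study". The Study Summary calls 4 mg the initial dose and says: "Flexible dosing of PER above 4mg to a maximum of 8 mg daily will be compared to use of alternative ASDs". It also provides for stepping down: "Reduction by 2 mg will be allowed in cases of efficacy if doses greater than 4 mg daily result in non-idiopathic side-effects".

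The secondary objective in section 2 writes the dose as a range: "PER treatment with a daily dose of 4 mg (up to -8mg". Section 7.3 names a single analysis population, the protocol-compliant one. Section 4.3 plans 10 subjects on adjunctive PER and 10 on alternative ASDs only, with the treating physician choosing the group.

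**The concern.** The endpoint names one dose, while the treatment under study is a range of doses. A patient who is on another permitted dose at 3 or 6 months and has a more than 50% reduction has responded to the assigned regimen, but on the literal wording has not responded on 4 mg. The plan does not say whether that patient is a responder, a non-responder, or outside the denominator.

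The dose at assessment is reached after assignment. The Study Summary allows reduction from doses above 4 mg because of side-effects, so dose depends at least partly on tolerability. An endpoint conditioned on it no longer describes the group as assigned, which is what the intent-to-treat sentence asks for. The alternative-ASD group has no matching dose condition, so a comparison would apply a filter to one arm only.

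At stake is the responder proportion that a pilot of this kind would hand to the larger trial. Two analysts could report different primary results from the same data, each with a sentence of the protocol in support.

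**Working it through.** There is no plan figure to reproduce. Section 7.1 sets 20 subjects as a feasibility target and gives no responder rate, effect size or power. The check compares sections and then adds simple arithmetic.

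**1. Timing.** Section 5.3 allows dosing up to 8 mg/day by 4 weeks, which is 28 days. The endpoint is read at 3 and 6 months, Days 90 and 180 in the Schedule of Events. Patients can therefore have left 4 mg before both readings.

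**2. Is 4 mg safely read as shorthand for the regimen?** The secondary objectives in the Study Summary and section 2 write out the range to 8 mg. Secondary Hypothesis 1 in 7.2 sets 4 against 8 mg/d as separate doses. Shorthand is possible, but an analyst could reasonably take 4 mg as meant.

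**3. Does anything else settle it?** Section 7.2 gives no counting rule by dose. Section 7.3 does not name an intent-to-treat set. Its protocol-compliant population adds a second conflict with 3.4.

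**4. Effect of one patient.** With n = 10 in the PER group (4.3), one responder on another dose is worth 1/10 = 10 percentage points.

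**5. Effect over a range.** Let p be the responder rate and e the share of the PER group not on 4 mg at assessment. Neither is in the documents. Both are assumed, and p is taken as the same at every dose.

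- Any permitted dose, all assigned: expected responders = 10p, out of 10.
- 4 mg only, others counted as non-responders: 10p(1 − e), out of 10.
- 4 mg only, others dropped: 10p(1 − e), out of 10(1 − e).

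| Assumed e | Assumed p | Any dose, of 10 | 4 mg only, of 10 | Denominator if others dropped |
|---|---|---|---|---|
| 0.2 | 0.3 | 3.0 | 2.4 | 8 |
| 0.2 | 0.5 | 5.0 | 4.0 | 8 |
| 0.2 | 0.7 | 7.0 | 5.6 | 8 |
| 0.5 | 0.3 | 3.0 | 1.5 | 5 |
| 0.5 | 0.5 | 5.0 | 2.5 | 5 |
| 0.5 | 0.7 | 7.0 | 3.5 | 5 |
| 0.7 | 0.3 | 3.0 | 0.9 | 3 |
| 0.7 | 0.5 | 5.0 | 1.5 | 3 |
| 0.7 | 0.7 | 7.0 | 2.1 | 3 |

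The gap between the first two counts is 10pe. It runs from 3.0 − 2.4 = 0.6 to 7.0 − 2.1 = 4.9 patients across the table. Dropping the others leaves the expected percentage at p only because p was assumed equal across doses; the denominator still shrinks. If response differs by dose, the percentage shifts too, by an amount that the documents do not allow one to compute.

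**The case against.** The best defence is that 4 mg is loose wording for the regimen: it is the initial dose in the Study Summary, the minimum in 5.2, and the dose that must be tolerated in 5.3. The Study Summary says that flexible dosing up to 8 mg is what will be compared with alternative ASDs. The primary hypothesis in 7.2 carries no dose condition. The intent-to-treat sentence could be read as resolving the ambiguity in favour of the whole group. The study is also a non-randomised pilot that 7.1 says is not powered for effectiveness.

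Much of this stands, and it rules out three stronger readings that a reader might infer.

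- **That the plan excludes patients above 4 mg.** No section says so. Exclusion is only the literal reading of one phrase.
- **That a count at 4 mg is selected on response.** No section says that escalation follows poor seizure control; the Study Summary refers only to best clinical practice. With entry at one seizure per 3 months (4.1) or one per month (3.1), four weeks also reveal little about response. Later escalation for poor control is plausible but is not stated. Only the link to tolerability is documented.
- **That the result would swing by a known amount, such as 30% against 60%.** Suppose 5 of 10 patients leave 4 mg and 3 respond in each half: the results are 3/10 = 30%, 3/5 = 60% and 6/10 = 60%. The counts are invented and response is equal in both halves, so the example shows no selection. The whole gap comes from counting the moved responders as failures, which no section prescribes.

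The defence does not remove the mismatch. The protocol writes the range where it means the range, treats 4 and 8 mg/d as distinct in 7.2, and gives no counting rule. Section 7.2 also sets a 0.05 significance threshold despite the pilot status, so the definition of a responder still matters.

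**Conclusion.** The point holds as an inconsistency in the primary endpoint. Its dose wording conflicts with the flexible regimen, and applied literally it also conflicts with the intent-to-treat sentence in the same section. The literal reading leaves out responders on other permitted doses and conditions the endpoint on a post-assignment variable.

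The firm size is 10 percentage points per affected responder, which rests only on the planned 10 PER subjects. The total effect is unknown because the documents do not give the number who will leave 4 mg; the expected counts above are illustrations under assumed p and e. The defect should be corrected before analysis, but it does not show that any patient will in fact be excluded. No view is taken on which dose is right.

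**What to change.** 1. In 3.4, define endpoint A as the number and proportion of all subjects assigned to each group, PER and alternate ASDs, with a more than 50% reduction in focal seizures at 3 and at 6 months. State that PER subjects are counted regardless of their dose at assessment and that those who have stopped PER are included. Naming both groups also supplies the comparison that the primary objective calls for.
2. Reconcile the dose wording of 3.4 with 5.2, 5.3 and the Study Summary.
3. Reconcile 7.3 with intent to treat, for example by making the protocol-compliant analysis supportive.
4. Say how a subject is counted when no seizure data exist at 3 or 6 months. Section 5.3 makes tolerating 4 mg a condition of staying in the study, and 4.4.2, despite its title, describes data storage and not outcome collection after withdrawal.

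The cost is a rewritten line in 3.4, a sentence or two in 7.3 and 4.4.2, and aligned dose wording. Dosing and the visit schedule do not change, and seizure diaries are already reviewed throughout follow-up.
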